Specific Aim: The purpose of the current study is to examine whether high dose N-acetylcysteine (NAC) blocks the adverse effects of increased kynurenic acid (KYNA) on selected measures of brain chemistry, function and behavior, through the inhibition of kynureine aminotransferase (KAT) II, which converts kynureine to KYNA. The study will be a double-blind, placebo-controlled, randomized cross-over challenge study, in which people with schizophrenia are pretreated with either high-dose NAC, 140 mg/kg up to a maximum of 15 g, or placebo, then receive tryptophan (TRYP), 6 gms. The tryptophan challenge method robustly increases peripheral measures of kynureine and KYNA in humans and putatively increases brain KYNA levels, through the CNS conversion of kynureine to KYNA; a process that is observed in both rodents and nonhuman primates. We will evaluate the ability of NAC to inhibit the conversion of kynureine to KYNA with the following primary outcome measures: 1) we will measure serum kynureine and KYNA before and after NAC/placebo pre-treatment and TRYP administration and examine whether NAC compared to placebo blocks the peripheral conversion of kynureine to KYNA; 2) we will use the arterial spin labeling (ASL) technique to measure whole brain and frontal gray matter cerebral blood flow (CBF) before and after NAC/placebo pre-treatment and TRYP administration and examine whether NAC compared to placebo attenuates the effects of TRYP on ASL CBF measures; 3) we will use magnetic resonance spectroscopy (MRS) to measure glutamate and glutathione levels in the medial prefrontal cortex (mPFC) before and after NAC/placebo pre-treatment and TRYP administration and examine whether NAC compared to placebo increases MRS glutathione and glutamate measures; and 4) we will use diffusion tensor imaging (DTI) to measure white matter fractional anisotropy (FA) before and after NAC/placebo pre-treatment and TRYP administration and examine whether NAC compared to placebo increases white matter FA.

We will have two secondary endpoints. First, if we observe that NAC attenuates the effects of TRYP on ASL and/or increases mPFC glutamate levels or white matter DTI FA, then we will examine whether these effects are related to changes in cognitive measures of attention, verbal and visual memory, and working

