memory. Second, we will examine the relationship of serum KYNA levels and kynurenine 3-monoxygenase (KMO) gene polymorphisms to the observed effects of NAC on our neuroimaging and cognitive outcome measures.

We hypothesize that NAC will inhibit KAT II, which will be reflected in the: 1) decreased peripheral conversion of kynurenine to KYNA; and 2) increased CBF, glutamate, and white matter fractional anisotropy (FA). In addition, we hypothesize that the NAC effects on the neuroimaging measures will be related to improved performance on cognitive measures of attention, verbal and visual memory and working memory. These observed effects of NAC will be greater than those seen with placebo. We further hypothesize that the NAC effects on ASL CBF, glutamate, and FA measures will be independent of NAC-induced changes in MRS glutathione, i.e., not due to the NAC oxidative stress mechanism, but, rather, will be correlated with NAC-induced reductions in the peripheral conversion of kynurenine to KYNA. Finally, we hypothesize that the observed effects of NAC on CBF, glutamate, and FA will be related to baseline serum KMO activity and KYNA levels. The demonstration that NAC reverses the adverse impact of increased KYNA levels will importantly support the development of KAT II inhibitors for the enhancement of cognition in schizophrenia.

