Challenge Phase (Visits 3 and 4): The Challenge Phase will utilize a double-blind, placebo-controlled, randomized cross-over design. A permuted block randomization system (block sizes 2 or 4) will be used to randomly assign participants to NAC, 140 mg/kg up to a maximum of 15 g, or placebo. There will be two Challenge Phase visits, which will be at least two weeks apart. On the day of each visit, participants will arrive at the MPRC Brief Stay Unit (BSU) at 7:15AM; all participants will have fasted since midnight. Participants are asked to avoid eating food of any kind after midnight the evening prior to visits 2 and 3. Participants are encouraged to drink water but to strictly avoid food, coffee, alcohol, and sodas. Participants who regularly use nicotine products will be given short breaks to use their products in order to avoid effects of nicotine withdrawal. The nicotine breaks will occur at least 60 minutes prior to the neuroimaging sessions in order to minimize the effect of nicotine on any of the neuroimaging measures. A heparin lock will be inserted for the repeated laboratory assessments and the initial clinical, cognitive, laboratory, and safety assessments will be conducted (including urine pregnancy test for female participants). Participants will then undergo their pre-treatment imaging studies. Upon completion of the imaging studies, participants will receive NAC, 140 mg/kg up to a maximum of 15 g, or placebo. They will receive the other study medication on the second visit (i.e., placebo or NAC). The proposed NAC dose has been used extensively to treat acetaminophen poisoning. We selected this high dose based on our preclinical studies showing high doses inhibit KAT II. There is extensive safety data available with this dose. We selected the effervescent formulation to minimize gastrointestinal and other side effects. In addition, the effervescent formulation is flavored, which helps to increase the tolerability and to mask the smell typically associated with NAC (46). Thirty minutes after NAC/placebo administration participants will receive TRYp, 6 grams in oral slurry form. The dose was chosen based on previous work showing cognitive effects to be associated with doses above 5 grams (47) and our the preliminary data from our previous Conte Center project, in which we demonstrated that TRYp (6 grams) produces a robust increase in KYNA and kynureine and reduction in the ASL measure of CBF in participants with schizophrenia and related disorders.

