Laboratory Assessments (1): kynureine pathway metabolites, inflammatory markers, oxidative stress and other related markers				
Nicotine Break (1)*		7:55 am	7:55 am	
Protein Free Snack				
Cognitive Measures (1): MCCB measures: HVLT-R, BACS Symbol Coding, BVMT, CPT-IP, WMS®-III, LNS;		8:00 am	8:00 am	
Clinical Assessments (1): BPRS, SANS, CDS, CGI		8:45 am	8:45 am	
Neuroimaging Studies (1)		9:15 am	9:15 am	
Nicotine Break (2)		10:30 am	10:30 am	
Oral Administration of N-acetylcysteine (NAC) 140 mg/kg up to a maximum of 15gm or placebo		10:35 am	10:35 am	
Oral Administration of Tryptophan 6 grams		11:05 am	11:05 am	
Lunch		11:25 pm	11:25 pm	
Vital signs, SEC, SSS		12:05 pm	12:05 pm	
Laboratory Assessments (2)				
Neuroimaging Studies (2)		12:20 pm	12:20 pm	
Laboratory Assessments (3)		1:35pm	1:35pm	
Protein Free Snack		1:40 pm	1:40 pm	
Nicotine break (3)				
Cognitive Measures (2)		1:55 pm	1:55 pm	

Clinical Assessments (2)		2:40 pm	2:40 pm	
Vitals, SEC, SSS		3:05 pm	3:05 pm	
Laboratory Assessments (4)				
Participant discharged. If participant has not returned to pre-challenge baseline, they will be reassessed every 30 minutes until ready		3:15 pm	3:15 pm	

*Nicotine breaks are optional and subject to occur at different times as long as they do not occur within 60 minutes prior to the neuroimaging studies.

**Due to the COVID-19 pandemic, the expired CO breathalyzer assessment is an optional procedure.

Randomization and Blinding: This will be a double-blind, placebo-controlled, randomized cross-over challenge study. Participant randomization will use a permuted block randomization system (block sizes 2 or 4), in which treatment assignment order is random within each block, with an equal number of participants assigned to each treatment, to generate a list of treatment assignments. Thus, it will be difficult to ascertain the next treatment assignment, even if a participant becomes unblinded, while any imbalance in the number of participants between the treatment groups will be kept within tight limits. All raters, investigators and other staff will be blind to treatment assignment except for the research pharmacist. The research pharmacist does not participate in assessing any of the primary symptom or side effect dependent variables and conveys no information about treatment assignment to participants or staff except in a medical emergency.

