Specific Aim #1: Peripheral KYNA will be measured prior and after treatment on both Challenge Phase visit days (i.e., N-acetylcysteine (NAC) and placebo). We will denote the Challenge Phase visit day as $d=1,2$, and the multiple measurement times on each day by $t=1, \dots, T$ for each participant i ($i=1, \dots, 100$). To test the hypothesis whether NAC compared to placebo blocks the peripheral conversion of kynurenone to KYNA, we will apply the multilevel mixed model to compare the changes of KYNA levels from baseline between the two treatment groups. The hierarchical random effects will include day and time points within a day. With a sample size of 100 participants and 20% attrition rate (i.e., 60 participants will complete the study), we will achieve power 80% to detect a small-medium effect size of Cohen's d 0.37 at the alpha level 0.05. In our previous study, the effect size of peripheral KYNA change (tryptophan vs. placebo) is $d= 4.77$. Thus, we will have ample power to detect the difference. The covariates including age, sex, and others will be examined and adjusted when necessary.

Specific Aim #2: To examine whether NAC compared to placebo attenuates the effects of tryptophan on ASL CBF measures, we will apply the mixed model to compare the changes of ASL CBF levels from baseline between treatment and placebo. The primary ASL outcome measure will be whole brain gray matter CBF. If significant, then we will perform additional analyses to examine whether specific cortical regions show group differences. The multiple comparison correction will be performed for the voxel level and cluster level inference using permutation test-based strategy (51). With a sample size of 100 participants and 20% attrition rate (i.e., 60 participants will complete the study), we will achieve power 80% to detect a small-medium effect size of 0.37 at the alpha level 0.05. In our previous study, the effect size of ASL whole brain gray matter CBF (tryptophan vs. placebo) was Cohen's $d=0.48$. Thus, we should have sufficient power to detect the difference. The covariates including age, sex, and others will be examined and adjusted when necessary.

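### Tryptophan is given on both challenge days, so the Aim 2 contrast estimates NAC versus placebo under a tryptophan load and cannot by itself show that NAC attenuates a tryptophan effect on CBF

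*Combined protocol and SAP*

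**What the plan says.** The Specific Aim section describes a two-condition cross-over in which participants are "pretreated with either high-dose NAC, 140 mg/kg up to a maximum of 15 g, or placebo, then receive tryptophan (TRYP), 6 gms". The Challenge Phase section confirms that tryptophan follows either pretreatment: "Thirty minutes after NAC/placebo administration participants will receive TRYp, 6 grams in oral slurry form". For the second visit it adds: "They will receive the other study medication on the second visit (i.e., placebo or NAC". The visit schedule lists "Oral Administration of Tryptophan 6 grams" at 11:05 am in both challenge-visit columns. No day omits tryptophan or replaces it with a placebo. The only tryptophan-free brain data are the scans taken before dosing on each day: "Participants will then undergo their pre-treatment imaging studies".

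The test for CBF is given under Data Analysis, Specific Aim #2: "To examine whether NAC compared to placebo attenuates the effects of tryptophan on ASL CBF measures, we will apply the mixed model", comparing change from baseline between treatment and placebo. The example model under Data Analysis has a treatment term, covariates and random effects. It has no tryptophan term and no NAC-by-tryptophan term.

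The intended conclusions are stronger. The Specific Aim section speaks of NAC blocking adverse effects of KYNA on the brain, and it makes attenuation of the tryptophan effect on ASL one of the triggers for the first secondary endpoint. The hypotheses paragraph ends: "The demonstration that NAC reverses the adverse impact of increased KYNA levels will importantly support the development of KAT II inhibitors".

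**The concern.** Attenuation is a compound claim: tryptophan lowered CBF in these participants, and NAC made that fall smaller because it acted on the tryptophan or KYNA effect. The plan tests neither part separately. The first is taken from an earlier study (tryptophan versus placebo, d = 0.48). The second is read off a contrast that would look the same if NAC raised CBF by some other route.

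Two things are at stake. A significant Aim 2 result could be reported as attenuation, and could open the first secondary endpoint on that footing, without support for the word. A null Aim 2 result could not be told apart from a challenge that failed to lower CBF, because no placebo-day CBF estimate is pre-specified.

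**Working it through.** **Inputs.** From Specific Aim #2: 60 completers, d = 0.37, alpha 0.05, stated power 80%, earlier tryptophan effect d = 0.48. Assumed: a two-sided paired t test, with d equal to the mean difference over the SD of the paired difference.

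**The plan's own figure.** Power is P(|t| > critical value) under a noncentral t with n − 1 degrees of freedom and noncentrality d√n. For n = 60 and d = 0.37, the noncentrality is 0.37 × √60 = 2.87 and power is 80.5%. The stated 80% is reproduced. It goes with 60 completers; the 80 that 20% attrition from 100 would leave gives 90.5%. That discrepancy is a separate matter.

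**What the contrast identifies.** Let T be the CBF change on the placebo + tryptophan day, N the effect NAC would have without tryptophan, and I the NAC-by-tryptophan interaction, which is the attenuation.

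- Placebo day: T
- NAC day: T + N + I
- Planned contrast: (T + N + I) − T = N + I

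T cancels, and N and I enter only as a sum. No analysis of these two conditions alone can split them.

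**Simulation of the planned test** (n = 60, 20,000 runs, paired-difference SD 1):

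| Assumed truth | T | N | I | Planned test rejects |
|---|---|---|---|---|
| A. True attenuation | −0.48 | 0 | 0.37 | 80.4% |
| B. Tryptophan active, NAC effect unrelated to it | −0.48 | 0.37 | 0 | 80.3% |
| C. Tryptophan inert, NAC effect direct | 0 | 0.37 | 0 | 80.5% |

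The three rates differ only by simulation error, as the algebra requires.

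**Would a placebo-day check settle it?** Consider the rule: declare attenuation if CBF falls on the placebo day and the NAC-minus-placebo difference is significant and positive. I assume change-score SD 1 and correlation 0.5 between days, so the paired-difference SD is again √(1 + 1 − 2 × 0.5) = 1.

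| Assumed truth | Rule met, significant fall required |
|---|---|
| A | about 78% |
| B | about 79% |
| C | about 2.5% |

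If a fall in sign alone is enough, the rule is met in about 46% of trials under C. A check that requires significance therefore guards against an inert challenge (C), but it does nothing to separate A from B.

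**Shared drift.** The schedule starts the scans at 9:15 am and 12:20 pm, 3 hours 5 minutes apart, with a nicotine break and lunch between them. The times are the same on both days. A common drift D turns the day means into T + D and T + N + I + D, and the difference is still N + I. Drift is a problem only for the placebo-day check, which would estimate T + D.

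**The case against.** The strongest defence is that the comparison is sound and the plan does address mechanism. Treatment order is randomized, the contrast is within participant, and Data Analysis states its overall goal neutrally as NAC-versus-placebo effects. The hypotheses paragraph expects NAC effects on CBF to be independent of the MRS glutathione change and correlated with reduced conversion of kynurenine to KYNA. Both are measured, and mediation analyses are planned. Placebo-day serum KYNA will show whether the biochemical challenge worked (earlier d = 4.77). An inert challenge also runs against the team's earlier CBF result at the same 6 g.

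Much of this stands, and it limits the point. A correlation with KYNA conversion and independence from glutathione would be useful evidence. They are, however, associations among post-randomization variables, and Data Analysis gives no model for the glutathione hypothesis. A rise in serum KYNA shows that the challenge reached the blood, not that CBF fell. The earlier result makes a CBF fall likely, but does not show it in this sample.

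A reader might infer more than the documents support:

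- **That the contrast is biased or its type I error inflated.** It is not. The gap is between estimate and wording.
- **That about 80% of trials would make a false claim.** That figure is the plan's own power under assumed values of T and N. The documents give no direct NAC effect on CBF and no tryptophan effect for this sample.
- **That the interval between scans distorts the result.** Drift common to both days cancels.
- **That all aims fail.** Aim 3 asks whether NAC increases its measures relative to placebo, and Aim 1 measures serum kynurenine and KYNA directly. The two conditions can answer both.
- **That a placebo-day fall would license the word attenuation.** Case B shows that it would not.

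**Conclusion.** The point holds for CBF and for the wording about blocking or reversing KYNA effects on the brain. The planned contrast equals N + I: a valid estimate of the NAC effect under a tryptophan load, but silent on whether that effect is attenuation. This follows from the design and needs no numerical assumption. The rejection rates (about 80% in all three cases) only illustrate it. They rest on 60 completers, a two-sided paired test and assumed effects of 0.37 and −0.48 or 0 on the paired-difference scale.

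The plan should be changed, because the intended conclusion and one trigger for a secondary endpoint rest on a word the test cannot support. The data and the primary comparison remain useful as they are.

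**What to change.** 1. **Wording.** State the Aim 2 conclusion, and the ASL part of the trigger for the first secondary endpoint, as a NAC-versus-placebo difference in CBF change under tryptophan load. Bring the blocking and reversing statements about the brain into line. State as a limitation that NAC without tryptophan was not studied.
2. **Challenge check.** Pre-specify the estimate, 95% CI and two-sided 0.05 test of the pre-to-post change in whole brain gray matter CBF on the placebo + tryptophan day. Report it beside the placebo-day rise in serum KYNA.
3. **Reading rule.** Treat a statistically significant placebo-day fall as necessary but not sufficient. Without it, make no statement about attenuation, and report a null contrast as uninformative about attenuation. With it, say only that a positive contrast is consistent with attenuation. Note that the check is uncontrolled for time of day, lunch and repeat scanning, and does not exclude a direct NAC effect.
4. **Mechanism models.** Pre-specify the models for independence from the MRS glutathione change and for association with the change in kynurenine-to-KYNA conversion. Label them supportive and non-randomized.

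The cost is revised text, one within-condition estimate and two supportive models, all from data already to be collected. No visit, scan or dose is added. The price is a narrower claim.

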In Exploratory Aim 2, we will evaluate whether the baseline KYNA and/or KMO activity levels can moderate the NAC effects in the Specific Aims 1-3 and Exploratory Aim 1. For the measurements in the Specific Aims 1-3, the interaction term between baseline KYNA and/or KMO activity and NAC treatment will be tested for the moderation effect. To examine whether baseline KYNA and/or KMO activity moderate the mediation pathways in Exploratory Aim 1, the nonparametric statistical inference (e.g. permutation tests and bootstrap inference) will be used due to relatively small sample size for the complex mediation and moderation model.

Potential Risks to the Participants:

Risks Related to N-acetylcysteine:

- Diarrhea. Somewhat likely and seriousness varies. If participants experience diarrhea they are free to end participation and may remain at the Research Center until they feel well enough to drive or someone can take them home. They will be instructed to drink fluids to remain hydrated.
- Flatulence. Somewhat likely and not serious. If participants experience flatulence they are free to end participation and may remain at the Research Center until they feel well enough to drive or someone can take them home.
- Nausea. Somewhat likely and not serious. If participants experience nausea they are free to end participation and may remain at the Research Center until they feel well enough to drive or someone can take them home.
- Vomiting. Somewhat likely and seriousness varies. If participants experience vomiting they are free to end participation and may remain at the Research Center until they feel well enough to drive or someone can take them home. They will be instructed to drink fluids to remain hydrated.
- Abdominal discomfort. Somewhat likely and not serious. If participants experience abdominal discomfort they are free to end participation and may remain at the Research Center until they feel well enough to drive or someone can take them home.
- Dysgesia. Not likely and not serious. If participants experience a change in their sense of taste they are free to end participation in the study and stop taking the study medication.
- Dizziness. Not likely and not serious. If participants experience dizziness they are free to end participation and may remain at the Research Center until they feel well enough to drive or someone can take them home.

- Rash (with or without fever). Not likely and not serious. If participants experience a rash, with or without fever, they are free to end participation and may remain at the Research Center until they feel well enough to drive or someone can take them home.

Risks Related to Tryptophan:

- Nausea, dyspepsia. Somewhat likely but not serious. In our previous experience with tryptophan, nausea was seen in 1 of 11 participants exposed to tryptophan. The participant vomited and then felt relief. If participants experience nausea they are free to end participation and may remain at the Research Center until they feel well enough to drive or someone can take them home.
- Vomiting. Somewhat likely and seriousness varies. If participants experience vomiting they are free to end participation and may remain at the Research Center until they feel well enough to drive or someone can take them home. They will be instructed to drink fluids to remain hydrated.
- Sleepiness. Somewhat likely and not serious. If participants experience sleepiness they are free to end participation and may remain at the Research Center until they feel well enough to drive or someone can take them home.
- Transient exacerbation of cognitive impairment and/or exacerbation of schizophrenia symptoms. Expected, not serious. We hypothesize a small, transient decrease in cognitive testing scores or worsening of schizophrenia after participants receive tryptophan. This impairment is on the order of magnitude one would expect when sleepy or distracted and will not impact any routine functioning. All participants are evaluated by trained medical staff prior to discharge to confirm a return to baseline. Any persisting symptoms or abnormal vitals will be reported to the study physician who will determine whether the participant is safe to be discharged. A return to baseline before discharge will be recorded in the participant's study documents.

Blood Draw:

- Infection or bruising at the blood draw site. Not likely, seriousness varied. The blood draw and IV catheter placement will be done by experienced nursing staff using universal precautions.

MR Scanning:

- Claustrophobia. Not likely, not serious. Participants will be screened prior to scanning. They can also abort the scanning procedure by squeezing a rubber signal ball. Research staff will be in communication with participants throughout the scanning.
- Thermal injury. Not likely, possibly serious. Participants will be screened prior to scanning for MR-incompatible materials.
- Backache. Somewhat likely, not serious. Participants who experience backache while lying in the scanner may abort the scanning procedure at any time.
- Temporary decrease in hearing after MRI. Not likely, not serious. The loud noises of the MRI machine may be loud enough to damage one's hearing. Participants will be fitted with ear plugs and/or headphones to reduce this risk. Participants may abort the scanning procedure at any time if they feel uncomfortable with the noise level.

- Nausea and vomiting. There may be a slight risk from taking the study compounds. If vomiting occurs inside the scanner, there is a risk of choking and that can be dangerous. Participants will be instructed to inform research staff if they feel nauseous before the scanning or anytime during the scan.

Miscellaneous:

- Boredom, Frustration. Somewhat likely, not serious. Participants may become bored or frustrated with interviews or testing. Participants may take breaks or end interviews/testing at any time- however, doing so may interfere with completion of the study and lead to early termination of participation.
- Loss of Confidentiality. Unlikely, potentially serious. All research participation carries the risk of loss of confidentiality. This is minimized by the research protocol's protections for participant data.

Adequacy of Protection against Risks: We will make every attempt to minimize all study-related risks. We will carefully monitor patients and psychiatric symptoms throughout the study

Confidentiality: Careful procedures will be used to protect the privacy of participants and the confidentiality of the data. Names will only appear on consent forms and on a master list that links them with study ID numbers (different from medical record numbers). This list will be stored in locked files in a separate location from the data. At the conclusion of the project, the list will be destroyed, unless continuation is planned and approved by the Institutional Review Board. All data (whether on forms or electronic data files) will be collected, analyzed, and reported according to the study ID number and will contain no names or other personal identifiers. Paper-based data will be stored in locked files. Electronic data files reside on desktop computers and are password protected.

Consenting: Potential participants will be identified through chart review or nomination by the treatment team. No participant will be approached for recruitment without approval of a primary clinician, who will determine suitability of the person for the protocol. A chart review will be completed for all nominated potential participants to reduce the likelihood that participants will be found ineligible after participating in more extensive assessment. The study interviewer will verify with the primary clinician that a potential participant is sufficiently stabilized to consider participation and has capacity to provide consent. This is done prior to the study interviewer approaching a potential participant. The study interviewer will be introduced to the potential participant and provide a brief overview of the project.

Research staff members are trained to recognize symptoms of severe mental illness and cognitive impairment that could undermine an individual's ability to provide informed consent. Interested participants will be provided study information and an informed consent form that contains all pertinent details of participation. As some potential participants will have poor reading skills, the consent form will be read aloud in tandem with their own silent reading of the document. Our research staff are carefully trained on obtaining consent from and interacting with people with seriously mentally illness and supervised by senior staff members. The individual securing consent will review any points about which the participant is unclear, and the participant will be invited to ask questions as needed. All participants who express willingness to provide consent will be queried about each paragraph of the agreement in order to ensure that they have adequate understanding of what they are agreeing to. Research staff are trained in strategies for interacting with people with severe mental illness, including speaking slowly and clearly, stopping to summarize frequently, and providing time for questions.

After reading the consent, and before obtaining a signature, a brief questionnaire, the Evaluation to Sign Consent (ESC), is administered to verify that the subject is competent to provide consent and has demonstrated comprehension of the consent document. The recruiter will also make a clinical judgment and not recruit participants who appear unable to grasp key aspects of the procedure. This approach, which requires a proactive demonstration on the part of the participant that they understand what is being requested,

has been used extensively at our sites. Per IRB regulations, a copy of the signed consent form is given to the participant, a copy is placed in the participant's medical record, and the original is kept in the laboratory. Research assistants obtaining informed consent will be experienced clinicians. They will receive detailed and standardized training as to how to obtain informed consent from people with severe mental illness. They will be observed obtaining informed consent from a potential participant by senior staff prior to being allowed to recruit on their own. Prior to signing the consent form, participants will be informed that participation in the study is contingent upon their meeting diagnostic criteria as determined in the clinical interview. All discussions with potential study participants will take place in a private room behind closed doors.

Potential Benefits of the Proposed Research to Participants and Others: By participating in this study there is no direct benefit to the study for the participant. However, we may improve understanding of illnesses that affect thinking and memory, and help physicians care for patients with such problems.

Importance of the Knowledge to be Gained: People with schizophrenia are characterized by marked cognitive impairments, which are major determinants of poor functional outcome in schizophrenia (54,55). Unfortunately, first and second generation antipsychotics have limited benefits for cognitive impairments (56,57), and studies of add-on pharmacological agents for the treatment of cognitive impairments have been largely disappointing to date (58-63). Cognitive remediation and other non-pharmacological strategies have shown some promise, but the observed beneficial effects rarely generalize beyond the measures included in the training exercises (64). In the absence of an effective treatment, cognitive impairments remain a critical unmet therapeutic need, and the demonstration that inhibition of KAT II leads to improved brain and cognitive function would represent a critically important development in the therapeutics of this disorder.

Our project is uniquely based on an emerging body of evidence, which suggests that disturbances in the kynureine pathway, especially those that lead to increased levels of KYNA, may be of critical importance in the pathophysiology of cognitive impairments in schizophrenia. Second, the proposed study is the first experimental test of brain and behavioral effects of KAT II inhibition in human subjects. The results from the study would provide unique insights into the mechanisms underlying the role of KYNA in the pathophysiology of schizophrenia. Third, although the use of NAC is not innovative, the hypotheses that: i) NAC may work through its ability to inhibit KAT II; ii) there may be large effects in a subgroup of people with schizophrenia, i.e., those characterized by high serum KYNA levels or low KMO activity; and iii) the use of high NAC doses (>5 times other clinical studies) are innovative. Fourth, in order to provide a comprehensive evaluation of the effects of NAC on various KYNA related manifestations of the illness, we will use a multi-dimensional evaluation of the effects of NAC on KYNA production in schizophrenia, which will include behavioral, biochemical, neuroimaging, and phenomenological assessments. Fifth, the parallel assessments across the two preclinical studies and two clinical studies will provide a framework to bi-directionally inform the interpretation of the results of these studies. The ability to translate the results across each of the proposed studies is critically important for the proposed Center. Finally, the demonstration that NAC blocks the impact of increased KYNA levels in people with schizophrenia will importantly support the development of KAT II inhibitors for the enhancement of cognition in schizophrenia.

References:

2. Miller, C. L., Llenos, I. C., Dulay, J. R., and Weis, S. (2006) Upregulation of the initiating step of the kynurene pathway in postmortem anterior cingulate cortex from individuals with schizophrenia and bipolar disorder. *Brain Res.* 1073-1074, 25-37. PMID: 16448631
